8.2.5 Clinical Laboratory and Urinalysis

Clinical laboratory assessments include hematology, clinical chemistry, coagulation, lipid panel, thyroid panel, LH, FSH, SHBG, renin, aldosterone, inhibin B for males only, and estradiol, prolactin, and progesterone for females only. eGFR for screening will be calculated from blood creatinine measured as part of screening clinical chemistry.

A complete list of study-required clinical laboratory and urinalysis tests is provided in [Section 13.3](#).

All study-required clinical laboratory tests must be conducted in accordance with the laboratory manual and will be performed by a central laboratory.

The Investigator must review the laboratory report, document the review, and record any clinically significant laboratory findings that occur during the study in the AE section of the eCRF. Laboratory reports must be filed with the source documents. Clinically significant laboratory findings are those that are not associated with the underlying disease, unless judged by the Investigator to be more severe than expected for the subject's condition.

All laboratory tests with values considered clinically significantly during the Treatment Period or within 30 days after the last dose of study drug should be reported as AEs and repeated at least weekly until the values return to normal or baseline or are no longer considered clinically significant by the Investigator or Medical Monitor. If such values do not return to normal/baseline within a period of time judged reasonable by the Investigator, the etiology should be identified and the Sponsor notified.

8.2.6 Psychiatric Evaluations

8.2.6.1 Columbia–Suicide Severity Rating Scale

The C-SSRS will be used during the study to monitor suicidal ideation and behavior. The C-SSRS is a Food and Drug Administration (FDA)–endorsed questionnaire administered by trained study personnel to screen for suicidality in trials of CNS-active compounds. The Baseline/Screening Version of the C-SSRS, which assesses both lifetime history and history from the last 12 months, will be used at screening to determine subject eligibility. The Since Last Visit Version of the C-SSRS will be used at all subsequent visits specified.

Refer to [Section 7.1.3](#) for suicidality individual treatment-stopping criteria.

8.2.6.2 Hospital Anxiety and Depression Scale

Subject anxiety and depression will be monitored during the study using the HADS, assessed at Weeks 6, 18, 30, 58, 70, and 76 ([Zigmond and Snaith 1983](#)). The HADS is a widely used subject-reported instrument that focuses on subjective disturbances of mood rather than physical signs. The scale consists of 14 items, 7 items each for anxiety and depression. Each item is rated on a 4-point scale based on the frequency of symptoms over the preceding week and ranging from 0 (not at all) to 3 (very often).

Refer to [Section 7.1.4](#) for depression and/or anxiety individual treatment-stopping criteria.

8.3 Adverse Events and Serious Adverse Events

8.3.1 Definition of Adverse Event

An AE is any untoward medical occurrence in a clinical trial subject who has signed the ICF; the event need not necessarily have a causal relationship with the study drug. Examples of AEs include but are not limited to:

- Clinically significant abnormal test results
- Clinically significant symptoms and signs
- Changes in physical examination findings
- Hypersensitivity
- Progression/worsening of underlying disease

A treatment-emergent adverse event (TEAE) is an AE that is temporally associated with administration of study drug and is defined as an AE that occurs during or after administration of the first dose of study drug of the Treatment Period until 30 days after the final dose of study drug (safety follow-up visit). For AEs that occur on the date of the first dose of study drug of the Treatment Period, the time of onset (before or after intake of study drug) must be specified.

An abnormal test result should be reported as an AE if any of the following criteria are met:

- Test result is associated with accompanying symptoms
- Test result requires additional diagnostic testing or medical/surgical intervention
- Test result leads to a change in study drug dosing or study drug discontinuation, significant additional concomitant drug treatment, or other therapy
- Test result is considered to be an AE by the Investigator or Sponsor

Merely repeating an abnormal test, in the absence of any of the above conditions, does not constitute an AE. Any abnormal test result that is determined to be an error does not require reporting as an AE.

Examples of events that do not meet the definition of an AE include but are not limited to:

- Clinically significant abnormal test result or other abnormal safety assessment associated with the underlying disease, unless it is more severe than expected for the subject's condition
- The underlying disease and its signs and symptoms, unless they are more severe than expected for the subject's condition
- Medical and surgical procedures; the condition that leads to the procedure is the AE if it meets the definition of an AE. For example, an acute appendicitis that begins during the AE reporting period should be reported as the AE, and the resulting appendectomy should be recorded as treatment for the AE.
- Anticipated day-to-day fluctuations of pre-existing disease(s) or condition(s) present or detected at the start of the study that do not worsen

8.3.2 Definition of Serious Adverse Event

An SAE or serious adverse drug reaction is any untoward medical occurrence at any dose that meets any of the following criteria:

- Results in death
- Is life threatening (immediate risk of death)
- Requires inpatient hospitalization or prolongation of existing hospitalization
- Results in persistent or significant disability/incapacity
- Is a congenital anomaly/birth defect
- Is an important medical event

Medical and scientific judgment should be exercised in determining whether an event is an important medical event. An important medical event may not be immediately life threatening and/or result in death or hospitalization. However, if it is determined that the event may jeopardize the subject and may require intervention to prevent one of the other outcomes listed in the definition above, the important medical event should be reported as serious. Examples of such events include allergic bronchospasm that requires intensive treatment in an emergency room or at home, blood dyscrasias or convulsions that do not result in hospitalization, or the development of drug dependency or drug abuse. If either the Sponsor or the Investigator believes that an event is serious, the event must be considered serious and evaluated by the Sponsor for expedited reporting.

Hospitalization does not include the following:

- Rehabilitation facilities
- Hospice facilities
- Respite care (eg, caregiver relief)
- Skilled nursing facilities
- Nursing homes
- Same-day surgeries (as outpatient/same day/ambulatory procedures)

Hospitalization or prolongation of hospitalization in the absence of a precipitating clinical AE is not in itself an SAE. Examples include the following:

- Admission for treatment of a pre-existing condition not associated with the development of a new AE or with a worsening of the pre-existing condition (eg, for workup of persistent pre-treatment lab abnormality)
- Social admission (eg, subject has no place to sleep)
- Administrative admission (eg, for yearly physical exam)
- Protocol-specified admission during a clinical trial (eg, for a procedure required by the trial protocol)
- Optional admission not associated with a precipitating clinical AE (eg, for elective cosmetic surgery)
- Pre-planned treatments or surgical procedures should be noted in the baseline documentation for the entire protocol and/or for the individual subject.

8.3.3 Classification of an Adverse Event

As far as possible, each AE will be described by the following:

- Duration (start and end dates)
- Severity ([Section 8.3.3.1](#))
- Relationship to study drug ([Section 8.3.3.2](#))
- Action(s) taken and, as relevant, the outcome ([Section 8.3.3.3](#))

8.3.3.1 Severity

The Investigator will assess the severity of each AE according to the National Cancer Institute CTCAE version 5.0 ([CTCAE 2017](#)), which is summarized in [Table 4](#).

Table 4. Severity of Adverse Events

Grade 1: Mild; asymptomatic or mild symptoms; clinical or diagnostic observations only; intervention not indicated.
Grade 2: Moderate; minimal, local, or noninvasive intervention indicated; limiting age-appropriate instrumental ADL (preparing meals, shopping for groceries or clothes, using the telephone, managing money, etc).
Grade 3: Severe or medically significant but not immediately life threatening; hospitalization or prolongation of hospitalization indicated; disabling; limiting self-care ADL (bathing, dressing and undressing, feeding self, using the toilet, taking medications, and not bedridden).
Grade 4: Life-threatening consequences; urgent intervention indicated.
Grade 5: Death related to AE.

Abbreviations: ADL, activities of daily living; AE, adverse event.

Note the distinction between the severity and the seriousness of an AE. A severe event is not necessarily a serious event. Severe is a category used for rating the intensity of an event, and both AEs and SAEs can be assessed as severe. For example, a headache may be severe (interferes significantly with subject's usual function) but would not be classified as serious unless it met at least one of the criteria for an SAE listed in [Section 8.3.2](#), such as resulting in hospitalization.

If there is a change in the severity of an ongoing AE, it will be recorded as part of the same event, with the worst grade of severity for the entire event timeframe being recorded.

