### **9.3.25 Adverse Events**

AEs are those AEs with onset date from the signing of the ICF until the end of the follow up period.

Treatment-emergent adverse events (TEAEs) are defined as any AEs, regardless of relationship to study drug, that have an onset or worsening in severity on or after the first dose of double-blinded study drug (within Treatment Period) until 30 days after the final dose of study drug (safety follow-up visit).

If a subject discontinues study drug but remains in the study, AEs with onset date after 30 days of last dose of study drug until the end of the follow up period will be considered post-treatment adverse events.

Related TEAEs are those reported by investigators as possibly related, probably related, or definitely related to the study drug.

AESIs are events that must be monitored on an ongoing basis as defined in Protocol Section 8.3.8 and identified in the AE eCRF page. The AESIs that are serious AEs (SAEs) will be handled according to guidelines from the National Cancer Institute Common Terminology Criteria for Adverse Events (CTCAE 2017) version 5.0, as described in Protocol Section 8.3.3.1.

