#### **14.1 Adverse Events**

All AE verbatim terms reported on the eCRFs will be coded using the Medical Dictionary for Regulatory Activities (MedDRA® version 23.0).

All reported AEs (including non-TEAEs) will be listed. Separate listings will be provided for SAEs, AESIs, and TEAEs leading to study drug discontinuation. For all TEAE tables, counting will be by subject and not by event. Additionally, if a subject reported the same TEAE on multiple occasions, the highest severity (severe > moderate > mild) or study drug relationship (related > probable > possible > unlikely > unrelated) recorded for the event will be summarized. All TEAE summary tables will present the number and percentages of subjects reporting TEAEs, unless otherwise specified. A summary of TEAEs by severity, seriousness, and relation to study drug will be tabulated.

AEs experienced during the Run-in Period will be reported separately. For Part A, AEs will be summarized by the actual randomized dose. For Part B, AEs will be summarized under the treatment at the onset of the AE. A subject who does-escalates in Part B will be counted within the denominator of each treatment group that s/he received. For example, a subject who started at 50 mg of tildacerfont, escalated to 100 mg of tildacerfont, and escalated again to 200 mg tildacerfont will be counted in all three dose levels; the AE that the subject experiences will be counted once under the dose level that the subject was taking at the onset of the AE. For Part C, all subjects will receive 200 mg tildacerfont.

An overall summary of AEs will be presented by study period (i.e., Part A, Part B, and Part C). The overall summary will include the number and percentage of subjects experiencing any AEs, study drug related AEs, AEs by maximum severity (highest toxicity grade), SAEs, study drug related SAEs, discontinued due to AE, and deaths.

The number and percentage of subjects experiencing each AE, study drug related AE, and SAEs will be summarized by treatment group according to system organ class and preferred term.

Additional table including only preferred term summarized by treatment for the number and percentage of subjects experiencing each AE will be presented as well

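### Adverse events that worsen after a dose switch are tabulated at their worst grade under the dose at onset, so severity by dose is misattributed

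*Protocol*

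**What the plan says.** **Collection.** Protocol 8.3.3.1 deals with an ongoing AE whose severity changes: "it will be recorded as part of the same event, with the worst grade of severity for the entire event timeframe being recorded". Protocol 8.3.3 lists what describes an AE. The timing item is "Duration (start and end dates)"; the others are severity, relationship, action and outcome. Neither a date of grade change nor a grade per period is listed.

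**Attribution.** SAP 14.1 has one rule per period:
- Run-in: "AEs experienced during the Run-in Period will be reported separately".
- Part A: "For Part A, AEs will be summarized by the actual randomized dose".
- Part B: "For Part B, AEs will be summarized under the treatment at the onset of the AE". For a subject who escalates, the AE is "counted once under the dose level that the subject was taking at the onset of the AE".
- Part C: the SAP notes only that everyone receives 200 mg.

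The overall summary includes "AEs by maximum severity (highest toxicity grade)". SAP 14.1.1 and 14.1.2 present severity, and moderate or severe treatment-emergent AEs (TEAEs), by period and dose.

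**TEAE definition.** SAP 9.3.25 counts AEs that "have an onset or worsening in severity on or after the first dose of double-blinded study drug". Protocol 8.3.1 and 8.3.4 define a TEAE by when it occurs, exclude AEs that occur before the first Treatment Period dose, and have no worsening clause. SAP Section 15 does not list this difference. SAP Section 4 lets the SAP govern where the two disagree.

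**The concern.** Each rule is conventional alone. Together they separate a grade from the treatment on which it was reached: the record holds one onset and one worst grade, and the tables place that grade by the onset.

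This matters more here than in a parallel-group trial with fixed treatment, because dose changes are built in for three of the four arms. Safety by dose is a main output of a dose-ranging study, and Part A is its only placebo-controlled safety comparison. Protocol 8.3.4 follows AEs until they resolve or stabilize, so a grade recorded against a Part A event may be one reached well after Part A. The protocol itself gives weight to grade changes: depression or anxiety may be an AE of special interest from Grade 2 (Protocol 8.3.8) and is a stopping criterion from Grade 3 (Protocol 7.1.4).

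**Working it through.** The plan states no figure on this point, so there is none to reproduce. The check is a cross-reading, with arithmetic only for scale.

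**1. Who changes treatment (Protocol 6.1.2, 9.2).** Placebo goes to 100 mg at Week 18. Subjects on 50 or 100 mg may be escalated after Weeks 18 and 24, and all are on 200 mg from Week 30. With 18 per group and 72 in total, the planned number who change at least once is 3 × 18 = 54 of 72. If the assumed dropout, 18 down to 15 per group, all came before the switch, it is 3 × 15 = 45. These are subjects who switch, not affected AEs.

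**2. Follow one AE through the rules (hypothetical).** A placebo subject has a Grade 1 AE in Part A. It is ongoing at Week 18 and becomes Grade 3 on 100 mg in Part B.

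| Step | Rule | Result |
|---|---|---|
| Record | Protocol 8.3.3.1 | one event, Grade 3 |
| Dates | Protocol 8.3.3 | start in Part A, and an end date |
| Period and dose | SAP 14.1 | Part A, placebo |
| Severity shown | SAP 14.1 | maximum, Grade 3 |
| Part B, 100 mg | SAP 14.1, counted once | nothing |

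The same happens to an AE that starts on 50 or 100 mg and worsens after escalation or after Week 30. That the start date stays unchanged is inferred from the event remaining the same event; the protocol does not say so in words.

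**3. Look for a rule that reassigns it.** SAP Section 14 assigns subjects who received different doses to a group from the time tildacerfont was received. It does not mention AEs that worsen, and the specific AE rule in 14.1 is onset. No other passage does so.

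**4. Do the same for the 200 mg arm.** An AE that starts at Grade 1 on 200 mg in Part A and becomes Grade 3 in Part B or C is also shown as Grade 3 in Part A, under 200 mg. The dose is right but the period is wrong. Later grades can therefore enter the Part A table in every arm.

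**5. Scale.** One event moves a group of 18 by 1/18 = 5.6 percentage points, two by 2/18 = 11.1, three by 3/18 = 16.7. This applies to the Part A groups. Part B denominators depend on escalation, since a subject counts at each dose received.

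**6. Run-in onset with later worsening.** Under SAP 9.3.25 this is a TEAE. Under Protocol 8.3.1 and 8.3.4 it is not. The SAP governs, but applying its clause requires knowing that the grade rose after the first double-blind dose. The items in Protocol 8.3.3 do not show that, and SAP 14.1 names no dose group for such an event.

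**The case against.** The strongest objection is that the case report form and its completion guideline are not among the documents. Protocol 8.3.3 is a general list, and the SAP's worsening clause suggests its authors expected worsening to be identifiable. This stands as a limit on the collection half: grade-change dates may already be held. It does not answer the attribution half, because SAP 14.1 still uses onset.

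Second, other outputs do not depend on the AE record. Laboratory results are summarized by actual treatment at each time point (SAP 14.2), the Hospital Anxiety and Depression Scale by time point and dose level (SAP 14.5.1), and vital signs and ECG thresholds by time point. Progression of a serious AE is reported as follow-up (Protocol 8.3.6), and AEs of special interest have narratives (Protocol 8.3.8). This stands and narrows what is at stake, especially for liver chemistry. The AE severity tables remain affected.

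Third, Part B escalation depends on the A4 result, so Part B comparisons by dose are not randomized in any case. True, but the tables will still be read as severity by dose.

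Fourth, closing an unresolved AE and opening a new one at the higher grade fits no outcome category in Protocol Table 6 and creates an artificial stop date. That stands, and the fix below avoids it.

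**Conclusion.** The point holds for AEs ongoing across the Week 18, 24 or 30 switch. As written, a grade first reached on tildacerfont, or on a higher dose, is tabulated under placebo or the lower dose and is absent from the dose on which it occurred. New-onset AEs are attributed correctly. The number affected cannot be estimated from the documents; the scale is 5.6 percentage points per event in a group of 18. The conclusion assumes that a continuing event keeps its start date and that sites follow Protocol 8.3.3.1. Separately, the two TEAE definitions conflict, and the SAP's version is workable only if the date of worsening is captured.

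A reader might infer three stronger things that the documents do not support:
- *That the Part A comparison is biased toward no harm.* Planned dose changes are only upward, which suggests it. But the 200 mg arm also carries later grades back into Part A, so the net direction is not established.
- *That the Part A severity table will change between the Week 18 and final analyses.* SAP 13.1 lists only efficacy analyses at Week 18, and SAP 13.2 places the safety endpoint at the final analysis. No earlier severity table is scheduled.
- *That the SAP leaves worsened run-in AEs in run-in.* SAP 9.3.25 makes them TEAEs. The difficulty is applying that rule, not its intent.

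**What to change.** - **Collection.** Keep the single AE record, and add the date and grade of each severity increase if the case report form does not already hold them.
- **SAP 9.3.25 and 14.1.** Count a worsening after the first double-blind dose, or after a dose change, as a TEAE at the higher grade under the period and dose at the date of worsening. Keep the grade reached before the switch under the onset dose. Apply the highest-severity rule within each period and dose.
- **Definitions.** Align Protocol 8.3.1 and 8.3.4 with SAP 9.3.25, and list the change in SAP Section 15.
- **Existing records.** Where the date of worsening cannot be recovered, use start and end dates to flag AEs ongoing across a switch, and show the severity tables with and without them.

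The cost is a few data items, short protocol and SAP wording, and some re-querying of AEs ongoing at a switch. Without the re-querying, earlier and later records would follow different conventions. If the case report form already captures the dates, the collection change falls away.

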8.3.3.2 Relationship to Study Drug

The Investigator will assess the relationship of each AE to study drug (or HC stress dosing) according to the categories in [Table 5](#). This assessment will serve to determine whether there exists a reasonable possibility that the study drug (or HC stress dosing) caused or contributed to the AE.

Table 5. Relatedness of Adverse Event to Study Drug (or HC Stress Dosing)

UNRELATED: This category applies to those AEs that are clearly and incontrovertibly due to extraneous causes (disease, environment, etc).

UNLIKELY RELATED: This category applies to those AEs that are judged to be unrelated to the study drug but for which no extraneous cause may be found. An AE may be considered unlikely to be related to the study drug if or when it meets two of the following criteria:
 
(1) it does not follow a reasonable temporal sequence in relation to administration of the study drug; (2) it could readily have been produced by the subject's clinical state, environmental or toxic factors, or other therapies administered to the subject; (3) it does not follow a known pattern of response to the study drug; or (4) it does not reappear or worsen when the study drug is re-administered.

POSSIBLY RELATED: This category applies to those AEs for which a connection to study drug administration cannot be ruled out with certainty. An AE may be considered possibly related if or when it meets two of the following criteria:
 
(1) it follows a reasonable temporal sequence in relation to administration of study drug; (2) it could not readily have been produced by the subject's clinical state, environmental or toxic factors, or other therapies administered to the subject; or (3) it follows a known pattern of response to the study drug.


PROBABLY RELATED: This category applies to those AEs that the Investigator thinks are related to the study drug with a high degree of certainty. An AE may be considered probably related if or when it meets three of the following criteria:
 
(1) it follows a reasonable temporal sequence in relation to administration of the study drug; (2) it could not be reasonably explained by the known characteristics of the subject's clinical state, environmental or toxic factors, or other therapies administered to the subject; (3) it disappears or decreases on cessation or reduction in dose of study drug. There are exceptions when an AE does not disappear upon discontinuation of the study drug yet drug-relatedness clearly exists (eg, as in bone marrow depression, fixed drug eruptions, or tardive dyskinesia); or (4) it follows a known pattern of response to the study drug.

DEFINITELY RELATED: This category applies to those AEs that the Investigator thinks are incontrovertibly related to the study drug. An AE may be assigned an attribution of definitely related if or when it meets all of the following criteria:
 
(1) it follows a reasonable temporal sequence in relation to administration of the study drug; (2) it could not be reasonably explained by the known characteristics of the subject's clinical state, environmental or toxic factors, or other therapies administered to the subject; (3) it disappears or decreases upon cessation or reduction in dose of study drug and recurs with re-exposure to the study drug (if re-challenge occurs); and (4) it follows a known pattern of response to the study drug.

Abbreviation: AE, adverse event.

The Investigator will use clinical judgment and consult the IB to determine the relationship. Alternative causes, such as underlying disease(s), concomitant therapy, and other risk factors, as well as the temporal relationship of the event to study drug (or HC stress dosing) administration will be considered and investigated.

AEs classified as unrelated or unlikely related will be considered not related to treatment, and AEs classified as possibly, probably, or definitely related will be considered related to treatment.

